## PARTICIPANT RECRUITMENT AND ENROLLMENT

### Eligibility Screening and Recruitment

The Nashville VA Institutional Review Board permits a record review to screen patients for research studies. Screening is conducted every weekday by the project coordinator or research assistant. The screening process starts with a structured query of the VISTA reporting system. The Physical Therapy Consult Report allows the study team to identify Veterans recommended for SNF care after hospital discharge. All Veterans on this report are added to the screening panel in the electronic medical record then reviewed for the following inclusion and exclusion criteria:

Inclusion Criteria: (1) Confirm that the Veteran is aged 50 years or older. (2) Next review the Essential Medication List Review to confirm the Veteran has 5 or more home medications excluding topical agents. (3) Review the inpatient social work admission note to verify that the Veteran speaks English, has a working telephone, and was admitted from the community (i.e., non-LTC location).

Exclusion Criteria: (1) The EMR is reviewed for indication of life expectancy less than 6 months by searching for palliative care consults with hospice recommendations, referrals to hospice agency, and diagnoses of Stage IV

cancer. (2) Lastly, the research flags are reviewed to determine whether the Veteran's current trial enrollment(s) include a pharmaceutical trial.

For Veterans who have multiple hospitalizations during the trial period, they are re-screened at each new admission to determine eligibility for participation.

## Enrollment Procedures

All Veterans meeting eligibility requirements are approached for consent. While any member of the research team can obtain informed consent, we preferred to have a study clinician, either Nurse Practitioner (NP) or Pharmacist (PharmD), provide an overview of the study and intervention in lay terminology. The Veterans and/or their surrogates were given time to review the study brochure and informed consent document then study personnel answered any questions. Prior to signing the consent documents, all Veterans were asked to complete a four question 'evaluation to sign consent' (approved by the IRB) to ensure they were capable of providing consent.

In the event that the Veteran was not capable of providing consent due to cognitive impairment, underlying comorbid conditions, or use of psychoactive medications, the study team sought the Veteran's legally authorized representative. In the case that a Veteran's inability to consent is temporary, the Veteran will be asked to provide verbal assent once they are deemed competent to consent. Participants will have full disclosure of who provided consent on their behalf and retain the right to re-consent or withdraw.

The process to obtain consent can occur in-person or via telephone. Study team's first preference is to meet with the Veteran and/or their surrogate in person.

1. However, in the event that study personnel cannot enter the Veteran's hospital room (due to COVID-19 precautions), the IRB approved a verbal consent process via the telephone in the Veteran's room. At the point the Veteran is no longer isolated, study staff will enter the room to provide the Veteran with a hardcopy of the study informed consent documentation and to have the Veteran sign a release of information form.
2. If the Veteran does not pass the evaluation to sign consent and their surrogate is not at the hospital, the IRB approved a verbal surrogate consent documentation. After verbal consent is given, study personnel mail a copy of the consent form to the surrogate for their records.

All enrolled Veterans will have a research flag placed in their medical record to identify them as a study participant. The research alert includes a brief description of the study and contact information for key study personnel. After enrolling, the Veteran will be added to an enrollment panel in the electronic medical record.

Following enrollment, Veterans are randomized to either intervention or control groups using the REDCap randomization feature which automatically assigns allocations based on a schedule (computer generated using Mersenne-Twister), which is uploaded by the team statistician. Veterans are randomized using permuted blocks of two or four where the size of each block is selected uniformly at random. This randomization ensures balance between the groups after every second or fourth randomization.

## STUDY PROCEDURES

Data collection includes Veteran descriptive data along with geriatric syndromes, medications, health status, safety, and implementation science as noted in the table below. Upon enrollment, the Veteran will complete interviewer-administered questionnaires (marked with an asterisk below) with interviews conducted by trained study personnel. In the event the Veteran is unable to complete assessments (e.g., delirious, cognitively impaired), their designated surrogate will be asked to complete the assessments for which surrogate responses have been validated. Assessments that can be completed by surrogates are the ICIQ (urinary incontinence), DETERMINE, falls, pressure ulcers, medication history, and demographics. The remainder of the data will be abstracted from each patient's medical record; however, total number and type of medications will be determined based on a

combination of patient interview, medical record and pharmacy refill history to ensure an accurate, complete medication list.

The data shown in the below table for the “SNF” column is abstracted from SNF medical records; thus, research personnel will not interview the participant again during their SNF stay. However, participants will be contacted via telephone by research personnel at 7 and 90 days after they leave the SNF. If the Veteran is willing to also complete our implementation evaluation interview to assess barriers and enablers of deprescribing during their routine 7-day follow-up call, we will conduct this additional interview at the current 7-day follow-up timepoint in conjunction with other 7-day assessments. However, in consideration of Veteran response burden, we will provide the Veteran with the option to schedule the implementation evaluation interview component anytime during the initial 14-days following SNF discharge, based on the preference and convenience of the Veteran, so that they may choose to complete this interview separately. Both the intervention and control group will be monitored using that same data collection schedule and measures.

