**Hypothesis 1d:** DROP will result in significantly fewer medications associated with geriatric syndromes at hospital discharge, SNF discharge and 90-days after SNF discharge.

**Specific Aim 2:** Document the effects of a Veteran-centered deprescribing intervention (DROP) on medication adherence, health status, and geriatric syndromes.

**Hypothesis 2a:** DROP will result in a significant improvement in medication adherence and self-rated health status at 7 and 90 days after SNF discharge.

**Hypothesis 2b:** DROP will result in a lower prevalence and severity of geriatric syndromes at 7 and 90 days after SNF discharge.

**Specific Aim 3:** Evaluate intervention implementation to inform future adoption and sustainability.

**Aim 3a:** Identify patient-level barriers and facilitators of DROP.

[figure not shown]
**Aim 3b:** Identify VA and Non-VA provider-level barriers and facilitators of DROP.

**Aim 3c:** Identify system-level factors that influence sustainability after hospital discharge.

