## Schedule of Assessments

Measures and Data Collection Timeline	Baseline Hospital	SNF Discharge	Post SNF Discharge	
			7-Days	90- Days
Descriptives			Telephone Interviews	
Demographics and Length of Stay	X	X		
Elixhauser Comorbidity Index	X			
Patient Attitudes Toward Deprescribing (PATD)*	X			X
Primary Outcome – Medications				
Total number and type of Routine and PRN Medications, including PIMs	X	X	X	X
Pharmacy Calls to Verify Refill History	X			X
Drug Burden Index (DBI)	X	X		X
Medication Adherence (ARMS)*	X		X	X
Secondary Outcome – Geriatric Syndromes				
Cognitive Impairment (BIMS)*	X		X	X
Delirium (BCAM)*	X		N/A	N/A
Depression (PHQ-9)*	X		X	X
Urinary Incontinence (ICIQ-UI SF)*	X		X	X
Unintentional Weight Loss (DETERMINE)*	X		X	X
Pain (Brief Pain Inventory, BPI-short form)*	X		X	X
Falls	X		X	X
Pressure Ulcers	X		X	X
Secondary Outcome – Health Status				
Functional Health Status (VES-13)*	X		X	X
Secondary Outcomes – Safety				
Unplanned Healthcare Utilization (hospitalizations, emergency room visits)		X	X	X
Adverse Drug / Withdrawal Events	X	X	X	X
Status: Long-Term Care, Hospice, Death		X	X	X
Implementation Evaluation				

Veteran & Provider Barriers and Facilitators	X		X	X
System-Level Factors related to Sustainability		X	X	X
Staff Time for Intervention Implementation	X	X	X	X
Stakeholder Input	X			

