### **Secondary Outcomes – Geriatric Syndromes, Medication Adherence, and Functional Status**

Delirium: is assessed via the Brief Confusion Method (bCAM), a screening tool validated for use with hospitalized older adults. If the participant screens positive for delirium, no other participant interviews are conducted. Members of the research team will re-assess delirium daily during the remainder of the hospitalization; if/when the Veteran screens negative, the remaining assessments will be administered to the Veteran. If delirium persists throughout the hospitalization, the Veteran's surrogate is approached for syndrome assessments. The bCAM is not repeated at any other time point as it cannot be completed via telephone.

Cognitive Impairment: is assessed by the Brief Interview for Mental Status (BIMS), which has a total score range from 0 to 15 (0-7: severe impairment; 8-12 moderate impairment; 13-15 cognitively intact).

Depression: The Patient Health Questionnaire-9 (PHQ-9) is a validated screen to assess for depressive symptoms and their severity. Each item is scored from 0 ("not at all") to 3 ("nearly every day") to produce a cumulative score between 0 (no depressive symptoms) and 27 (severe depressive symptoms). If a Veteran reports severe depression or thoughts of self-harm, the study team elicits more information on their immediate safety then contacts the primary treatment team to close the loop for follow-up. The study team also offers to connect the Veteran with the VA's emergency helpline.

Urinary Incontinence: The International Consultation on Incontinence Questionnaire – Urinary Incontinence Short Form (ICIQ-UI SF) has four components and measures symptoms, frequency, and impact of urinary incontinence on quality of life. This tool has well established reliability and validity including sensitivity to treatment.

Unintentional Weight Loss and Poor Appetite: Nutritional concerns are assessed through the Determine Your Nutritional Health checklist, which is a 10-item tool utilized by the state government to determine nutritional risk in older adults receiving meal assistance. The checklist has 10-items which yields a nutritional risk score of 0-2 (low), 3-5 (moderate), and  $\geq 6$  (high). One item asks if they experienced a 10-pound weight change; if the Veteran indicates they had experienced a weight change, the study team will ask a structured question to clarify if the weight change was a gain or a loss.

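### A Veteran reached at follow-up who cannot be interviewed because of cognition has no route to a BIMS value, so the Hypothesis 2b cognitive endpoint treats an outcome-caused gap as missing at random

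*Combined protocol and SAP*

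**What the plan says.** All places are in the combined protocol and SAP.

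- **Endpoint.** Hypothesis 2b (Overview and Objectives): "DROP will result in a lower prevalence and severity of geriatric syndromes at 7 and 90 days after SNF discharge". Cognitive impairment is one of these syndromes and is measured by the BIMS.
- **Who answers when the Veteran cannot.** Study Procedures: "In the event the Veteran is unable to complete assessments (e.g., delirious, cognitively impaired), their designated surrogate will be asked". The permitted assessments are then listed: "Assessments that can be completed by surrogates are the ICIQ (urinary incontinence), DETERMINE, falls, pressure ulcers, medication history, and demographics". The BIMS is not among them.
- **Mode and timing.** In the Schedule of Assessments the row "Cognitive Impairment (BIMS)" carries the asterisk for interviewer-administered questionnaires. It is due at baseline, 7 days and 90 days, with nothing at SNF discharge.
- **Scoring.** The BIMS is a tool "which has a total score range from 0 to 15 (0-7: severe impairment; 8-12 moderate impairment; 13-15 cognitively intact"). No value is defined for a test that could not be done.
- **Persistent delirium in hospital.** The Veteran's "surrogate is approached for syndrome assessments", but the surrogate has no BIMS to complete.
- **Analysis.** Outcomes, Hypothesis 2b: mixed-effects logistic regression for prevalence and mixed-effects proportional odds regression for severity, with no rule for Veterans who cannot be tested.
- **Missing data.** Missing Data section: missingness is compared by group, and multiple imputation follows as a sensitivity analysis only if an imbalance is found.

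**The concern.** At the follow-up calls, one reason for a missing BIMS is the condition that the BIMS measures. Such a Veteran is impaired, yet the plan supplies neither a score nor a category. The models then let scores from Veterans who could be tested stand in for the missing one.

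Two things are at stake. Prevalence and severity are probably understated. The comparison of arms can also be distorted, because DROP aims to lower anticholinergic and sedative burden, and the Background links drug burden to long-term cognitive impairment and delirium. If the intervention changes who is testable, in either direction, a comparison of tested Veterans is a comparison of groups selected after randomization. The plan also leaves the handling of these Veterans open until the data have been seen.

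**Working it through.** **1. Is there any route to a value?** Four routes were checked for a Veteran who is reached but cannot be interviewed because of cognition.

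| Route | What the plan provides |
|---|---|
| Surrogate | The BIMS is not on the list (Study Procedures) |
| Medical or SNF record | The BIMS is an interview item with no SNF-discharge value (Schedule of Assessments) |
| Inability code | None; only 0-15 and three bands (Description of Assessments) |
| Analysis rule | None in Hypothesis 2b; imputation only on imbalance (Missing Data) |

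No route exists.

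**2. Is there a figure to reproduce?** No rate of untestable Veterans is given. The only power statement covering this endpoint is above 93% with 260 Veterans, and it cannot be reproduced because no effect size, event rate or alpha is stated.

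**3. Illustration under assumptions.** Let p be the share impaired when untestable Veterans count as impaired, and u the share reached but untestable because of cognition. Tested-only prevalence is (p − u)/(1 − u). Assume p = 40% in controls and 30% with DROP. The true odds ratio is (0.30/0.70)/(0.40/0.60) = 0.64 and the difference is 10.0 points.

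| u control / DROP | Tested-only control v DROP | Difference (points) | Odds ratio |
|---|---|---|---|
| 5% / 5% | 36.8% v 26.3% | 10.5 | 0.61 |
| 10% / 10% | 33.3% v 22.2% | 11.1 | 0.57 |
| 15% / 15% | 29.4% v 17.6% | 11.8 | 0.51 |
| 10% / 5% | 33.3% v 26.3% | 7.0 | 0.71 |
| 15% / 5% | 29.4% v 26.3% | 3.1 | 0.86 |
| 5% / 10% | 36.8% v 22.2% | 14.6 | 0.49 |

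For the 10% / 10% row: (0.40 − 0.10)/0.90 = 33.3% and (0.30 − 0.10)/0.90 = 22.2%. Control prevalence falls from 40% to between 29% and 37%. The odds ratio moves away from 1 in some rows and towards 1 in others.

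**4. A case where tested prevalence is equal.** Let q be the prevalence among the tested, assumed 30% in both arms, so that full prevalence is u + (1 − u)q. With u = 12% v 6%: 0.12 + 0.88 × 0.30 = 38.4% and 0.06 + 0.94 × 0.30 = 34.2%, a difference of 4.2 points where the tested-only result shows none. With u = 8% v 4% it is 35.6% v 32.8%, or 2.8 points.

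**5. Would the imbalance check catch it?** Equal u is not an imbalance, so rows 1 to 3 would not trigger imputation. For 12% v 6%, Fisher's exact test gives p = 0.13 with 16 v 8 of 130 per arm, and p = 0.28 with 10 v 5 of 85 per arm. The 85 is an assumption: the plan's original retention applied to 260, 260 × 354/540 = 170, halved. The plan states no criterion for imbalance; one based on significance could miss this.

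**The case against.** - **The plan nowhere says that these Veterans are dropped.** True; it follows from the absence of every alternative.
- **A reader might infer that the worst cognitive outcomes in general are lost.** The documents do not support that. A Veteran who attempts the BIMS and fails falls in the 0-7 band and counts as severely impaired. The only written stop rule is a positive delirium screen in hospital, and that screen is not repeated at follow-up.
- **The surrogate rule is worded for enrollment.** True, and its extension to the calls is a reading. But surrogates are used at follow-up for falls and pressure ulcers, and no other route to a BIMS value is given there.
- **A reader might infer that the affected group is large, because Veterans are enrolled through a representative when** "In the event that the Veteran was not capable of providing consent due to cognitive impairment". This does not follow. Incapacity to consent has other listed causes and can be temporary, delirious Veterans are re-assessed daily, and admissions from long-term care are excluded.
- **The Missing Data section already covers this.** In part. It allows that missingness may relate to the intervention and acts on imbalance, so a reader who infers that any arm-related effect would be invisible goes too far. But it acts only on imbalance, and standard imputation assumes missing at random.
- **The mixed model uses the Veteran's own scores at other visits; the illustration uses crude single-time proportions.** This stands. Earlier scores help where decline was already visible. They do not help where no score exists or decline came afterwards.
- **The effect would change no conclusion.** For 38.4% v 34.2% at 85 per arm, the standard error is 7.4 points, z = 0.57, and the 95% interval is about −10 to +19 points. That bears on how much weight the point deserves, not on whether the estimate is biased.

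**Conclusion.** The point holds for a limited group: Veterans contacted at 7 or 90 days who cannot be interviewed at all because of cognition. For them the outcome causes the missingness, and neither the Hypothesis 2b models nor the conditional imputation allows for that. Prevalence and severity of cognitive impairment are probably understated, and the arm comparison may be biased in either direction.

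The size is unknown. The tested-only odds ratios of 0.49 to 0.86 against a true 0.64 rest on assumed prevalences and assumed untestable shares of 5% to 15%, and they do not represent the planned repeated-measures model. The conclusion also rests on reading the surrogate rule as applying to the calls. It concerns one secondary endpoint; the primary outcomes are unaffected.

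**What to change.** 1. At each call, record why the BIMS was not done, using fixed written criteria: unable because of cognition, unable for another reason (such as hearing), refused, or not reached. If follow-up is complete, take the reason from existing call notes. Classify it blind to arm where possible: the calls are led by the clinician role that delivers the intervention, and blinding is stated only for event adjudicators. The SNF record cannot supply the reason, because it predates both calls.
2. State in the BIMS description and in the Hypothesis 2b analysis that a Veteran contacted but unable because of cognition counts as impaired for prevalence and in the 0-7 category for severity. Leave inability for any other reason as missing.
3. Report the tested-only analysis alongside in all cases, whether or not missingness differs by arm.

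The cost is one reason field on the call form, or a review of notes, and a short addition to the SAP. The downside is some misclassification, for example transient delirium or a reason that is uncertain or judged unblinded. The tested-only result shows how much the coding matters.

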## Schedule of Assessments

Measures and Data Collection Timeline	Baseline Hospital	SNF Discharge	Post SNF Discharge	
			7-Days	90- Days
Descriptives			Telephone Interviews	
Demographics and Length of Stay	X	X		
Elixhauser Comorbidity Index	X			
Patient Attitudes Toward Deprescribing (PATD)*	X			X
Primary Outcome – Medications				
Total number and type of Routine and PRN Medications, including PIMs	X	X	X	X
Pharmacy Calls to Verify Refill History	X			X
Drug Burden Index (DBI)	X	X		X
Medication Adherence (ARMS)*	X		X	X
Secondary Outcome – Geriatric Syndromes				
Cognitive Impairment (BIMS)*	X		X	X
Delirium (BCAM)*	X		N/A	N/A
Depression (PHQ-9)*	X		X	X
Urinary Incontinence (ICIQ-UI SF)*	X		X	X
Unintentional Weight Loss (DETERMINE)*	X		X	X
Pain (Brief Pain Inventory, BPI-short form)*	X		X	X
Falls	X		X	X
Pressure Ulcers	X		X	X
Secondary Outcome – Health Status				
Functional Health Status (VES-13)*	X		X	X
Secondary Outcomes – Safety				
Unplanned Healthcare Utilization (hospitalizations, emergency room visits)		X	X	X
Adverse Drug / Withdrawal Events	X	X	X	X
Status: Long-Term Care, Hospice, Death		X	X	X
Implementation Evaluation				

Veteran & Provider Barriers and Facilitators	X		X	X
System-Level Factors related to Sustainability		X	X	X
Staff Time for Intervention Implementation	X	X	X	X
Stakeholder Input	X			

## Description of Assessments

Demographic and Administrative Data: The sociodemographic data is obtained primarily obtained from medical record abstraction then verified with the Veteran (or their surrogate). Using a standardized abstraction form, study personnel collects and records age, gender, race, ethnicity, home address, telephone number, insurance status, outpatient providers, and pharmacies. We also abstract key information related to this hospitalization including site prior to hospitalization, admission date, admission diagnoses, hospital service/team, and discharge date and disposition. Data is verified with the Veteran, and participants are also asked their highest level of education and complete the Brief Health Literacy Screen.

GerontoNet Adverse Drug Event risk assessment calculated the Veteran's risk for experiencing an adverse drug event. The assessment contains items related to certain comorbid conditions or diagnoses, which are assessed via the Veteran's problem list. The other component is previous adverse drug reactions, which are assessed in the baseline demographic interview.

Walter Index is a prognostic tool to predict mortality within one year of hospital discharge. A higher score indicates a greater likelihood of mortality. The components of this tool are comorbid conditions and lab values which are abstracted from the Veteran's problem list and hospital intake assessment. The component assessing assistance with activities of daily living is completed by both medical records review (physical therapy notes) and during the baseline demographic interview.

Patients' Attitudes Toward Deprescribing (PATD) is a 15-item survey of which the first 10 items are part of a 5-point Likert scale ranging from 'strongly agree' to 'strongly disagree.' Examples include: "I feel that I am taking a large number of medicines" and "I believe that all my medications are necessary." The remaining five questions are related to patient's perception of their total number of medications, history and comfort level with stopping a medication. If the patient is unable to answer, the questionnaire can be administered to the surrogate.

